## 4. Study Objectives

Objectives	Endpoints
Primary	

 
To evaluate in patients having achieved a state of sustained remission, whether the combined ixekizumab treatment group is superior to the placebo group in maintaining response during Period 2
 
	
 
The proportion of patients in the randomized withdrawal population who do not experience a flare during Period 2
 

Major Secondary	

 
To evaluate in patients having achieved a state of sustained remission whether the ixekizumab 80 mg every 4 weeks (Q4W) treatment group is superior to placebo in maintaining response after randomized withdrawal
 
	
 
The proportion of patients in the randomized withdrawal population who do not experience a flare during Period 2
 

 
To evaluate in patients having achieved a state of sustained remission whether the combined ixekizumab treatment group is superior to the placebo group in maintaining response after randomized withdrawal
 
	
 
Time to flare for patients in the randomized withdrawal population during Period 2
 

 
To evaluate in patients having achieved a state of sustained remission whether the ixekizumab 80 mg Q4W treatment group is superior to placebo in maintaining response after randomized withdrawal
 
	
 
Time to flare for patients in the randomized withdrawal population during Period 2
 

Other Secondary	

 
To evaluate in patients having achieved a state of sustained remission whether the combined ixekizumab treatment group, ixekizumab 80 mg Q4W or ixekizumab 80 mg Q2W is superior to the placebo group in maintaining response during Period 2
 
	
 
The proportion of patients in the randomized withdrawal population with a 20% improvement in the Assessment of Spondyloarthritis International Society criteria (ASAS20), a 40% improvement (ASAS40), and improvement of at least 20% and improvement of at least 1 unit in at least 5 of 6 domains in the ASAS (ASAS5/6), ASAS partial remission, clinically important improvement (change of Ankylosing Spondylitis Disease Activity Score [ASDAS] <math>\geq 1.1</math> units), major improvement (change of ASDAS <math>\geq 2.0</math> units), inactive disease (ASDAS <math>< 1.3</math>), and ASDAS <math>< 2.1</math> during Period 2
 
Change from baseline in the individual components of the ASAS response criteria
 
Change from baseline in Bath Ankylosing Spondylitis Disease Activity Index (BASDAI)
 
Proportion of patients with Bath Ankylosing Spondylitis Disease Activity Index 50 (BASDAI50) response from baseline
 
Change from baseline in ASDAS
 
Change from baseline in high sensitivity C-reactive protein (CRP)
 
Change from baseline in Bath Ankylosing Spondylitis Functional Index (BASFI)
 
Change from baseline in the measures of axial mobility: 
 
Bath Ankylosing Spondylitis Metrology Index (BASMI) (linear), and BASMI individual components
 
Chest expansion
 
Change from baseline in occiput to wall distance
 
 
 
Change from baseline in Maastricht Ankylosing Spondylitis Enthesitis Score (MASES) and Spondyloarthritis Research Consortium of Canada Score (SPARCC) enthesitis score
 

Other Secondary	
	
 
The recovery (Tender Joint Count [TJC]=0, Swollen Joint Count [SJC]=0) and change from baseline of peripheral arthritis by TJC and SJC of 46/44 joints
 
The incidence rate of anterior uveitis or uveitis flares since baseline
 
Change from baseline in the following health outcomes measures: 
 
Fatigue numeric rating scale (NRS) score
 
Quick Inventory of Depressive Symptomatology Self-Report-16 (QIDS-SR16)
 
36-item Short Form Health Survey (SF-36), both physical and mental component scores
 
Assessments of Spondyloarthritis International Society–Health Index (ASAS HI)
 
European Quality of Life - 5 Dimensions 5 Level (EQ-5D-5L)
 
Work Productivity Activity Impairment-Spondyloarthritis (WPAI-SpA)
 
Jenkins Sleep Evaluation Questionnaire (JSEQ)
 
 
 

 
To assess the combined ixekizumab treatment group, ixekizumab 80 mg Q4W or ixekizumab 80 mg Q2W for 2-year radiographic progression in spine in patients with active radiographic axSpA (rad-axSpA)
 
	
 
Change in modified Stoke Ankylosing Spondylitis Spinal Score (mSASSS score) from baseline of originating study
 
Proportion of patients with change in mSASSS score <2 from baseline of originating study to Week 56 in RHY
 
Proportion of patients with no new syndesmophyte formation from baseline of originating study to Week 56 in RHY
 

 
To assess the efficacy of retreatment with ixekizumab following a flare during Period 2
 
	
 
Proportion of patients who regain ASDAS <1.3 within 16 weeks after ixekizumab retreatment
 
Proportion of patients who regain ASDAS <2.1 within 16 weeks after ixekizumab retreatment
 
Proportion of patients who achieve/maintain an ASAS20, ASAS40, ASAS5/6, ASAS partial remission, ASDAS major improvement, ASDAS clinically important improvement, ASDAS inactive disease, and ASDAS <2.1 within 16 weeks after ixekizumab retreatment
 
Proportion of patients who achieve/maintain an ASAS20, ASAS40, ASAS5/6, ASAS partial remission, ASDAS major improvement, ASDAS clinically important improvement, ASDAS inactive disease, and ASDAS <2.1 through Week 64
 


 
To determine the long-term treatment effect of 80 mg ixekizumab Q2W and 80 mg ixekizumab Q4W through Week 104
 
	
 
The proportion of patients with ASAS20, ASAS40, ASAS 5/6, ASAS partial remission, clinically important improvement, major improvement, ASDAS <2.1, and inactive disease
 
Change from baseline in the individual components of the ASAS criteria
 
Change from baseline in BASDAI
 
Proportion of patients with BASDAI50 response
 
Change from baseline in ASDAS
 
Change from baseline in CRP
 
Change from baseline in BASFI
 
Change from baseline in the measures of axial mobility: 
 
BASMI (linear), and BASMI individual components
 
 
 

Other Secondary	
	
 
○ Chest expansion
 
○ Change from baseline in occiput to wall distance
 
● Change from baseline in MASES and SPARCC
 
● The recovery (TJC=0, SJC=0) and change from baseline of peripheral arthritis by TJC and SJC of 46/44 joints
 
● The incidence rate of anterior uveitis or uveitis flares
 
● Change from baseline in the following health outcomes measures: 
 
○ Fatigue NRS score
 
○ QIDS SR16
 
○ SF-36 (both physical and mental component scores)
 
○ ASAS HI
 
○ EQ-5D-5L
 
○ WPAI-SpA
 
○ JSEQ
 
 
 

● To evaluate the development of anti-ixekizumab antibodies and its impact on the efficacy of ixekizumab	
 
● Efficacy response rates listed below at Weeks 64 and 104 by treatment-emergent anti-drug antibody (TE-ADA) status and by neutralizing anti-drug antibody (NAb) status: 
 
○ Proportion of patients achieving ASAS40
 
○ Proportion of patients achieving ASAS20
 
○ Proportion of patients achieving ASDAS <2.1
 
 
 

CCI

## 5. Study Design

This section contains the summary of study design, the method of treatment assignment, and the sample size determination from the protocol for Study I1F-MC-RHBY (RHBY).

### 5.1. Summary of Study Design

Study RHBY is a Phase 3, multicenter, long-term extension study that includes a double-blind, placebo-controlled, randomized withdrawal-retreatment (RWR) period. The study duration will be up to 2 years for ixekizumab administration, and up to 2 years and 6 months for study participation over 4 study periods:

- Lead-In [**Period 1**]: 24 weeks (Week 0 to Week 24)
- Extension Period including Double-Blind, Placebo-Controlled, Randomized Withdrawal-Retreatment [**Period 2**]: 40 weeks (Week 24 to Week 64)
- Long-Term Extension Period [**Period 3**]: 40 weeks (Week 64 to Week 104)
- Post-Treatment Follow-Up [**Period 4**]: at least 12 weeks and up to 24 weeks after the date of the patient's early termination visit [ETV] or last regularly scheduled visit).

Patients who completed an originating study (RHBV, RHBW, or RHBX) through Week 52 may be eligible for enrollment into Study RHBY provided they fulfill study entry criteria for Study RHBY (see Protocol Section 6).

Study RHBY will evaluate the sustainability of clinical benefits, safety, and tolerability of ixekizumab treatment as well as the impact of ixekizumab on structural progression in patients with axial spondyloarthritis (axSpA). In addition, maintenance of response after treatment withdrawal will be evaluated in those patients having achieved a state of sustained remission, defined as 1 of the following:

- Ankylosing Spondylitis Disease Activity Score (ASDAS) <1.3 at Week 16 and Week 20.  
OR
- ASDAS <1.3 at Week 16 and ASDAS <2.1 at Week 20  
OR
- ASDAS <2.1 at Week 16 and ASDAS <1.3 at Week 20.

Figure RHBY.5.1 illustrates the study design. During the 24-Week Lead-In Period [Period 1], all patients will receive active treatment in the form of ixekizumab 80 mg every 4 weeks (IXE80Q4W) or ixekizumab 80 mg every 2 weeks (IXE80Q2W).

**[Group A]:** Patients who DO NOT meet entry criteria for participation in the 40-week double-blind placebo-controlled RWR period will continue to receive the ixekizumab dose regimen that they are receiving at Week 24 during Periods 2 and 3.

**[Group B]:** For patients who DO meet entry criteria for participation in the 40-week double-blind, placebo-controlled RWR period (that is, patients having achieved a state of sustained remission),

- Patients in the ixekizumab 80 mg Q2W treatment group (IXE80Q2W) will be re-randomized to either IXE80Q2W or placebo at 2:1 ratio and will be stratified by geographic region (see [Table RHBY.6.2](#)) and originating study.
- Patients in the ixekizumab 80 mg Q4W treatment group (IXE80Q4W) will be re-randomized to either IXE80Q4W or placebo at 2:1 ratio and will be stratified by geographic region (see [Table RHBY.6.2](#)) and originating study.

After completion of the 40-week RWR period, patients will continue the same treatment that they are receiving at the end of Period 2, and will continue in the Long-Term Extension Period (Period 3).

Patients who have taken at least 1 study dose and who discontinue study treatment are to complete an early termination visit (ETV) and enter into Post-Treatment Follow-Up Period (Period 4) for at least 12 weeks and up to 24 weeks after the ETV date or the last regularly scheduled visit. Patients whose ETV or last regularly scheduled visit is longer than 12 weeks after their last study dose are not required to enter into the Post-Treatment Follow-Up Period.

[figure not shown]

Figure RHBY.5.1. Illustration of study design for Clinical Protocol I1F-MC-RHBY.

(footnotes on next page)

Abbreviations: Q2W = once every 2 weeks; Q4W = once every 4 weeks; W = week.

- a Patients in Group A will continue to receive the same ixekizumab dose regimen that they were receiving during Period 1.
- b Only patients having achieved a state of sustained remission (Group B) are eligible for participation in the randomized withdrawal–retreatment period.
- c Patients who experience a flare will be retreated with the ixekizumab treatment regimen that they were receiving prior to withdrawal. Flare status is determined by ASDAS score ([Table RHY.6.4](#)). The interactive web-response system uses the flare status to dispense drug. Therefore, no missing data is allowed before discontinuation. If a component score is missing (eg, missing C-reactive protein due to COVID-19 mitigation plan) at an intermittent visit, the last nonmissing score is carried forward for the assessment.
- d As of Week 64, patients receiving ixekizumab 80 mg Q4W during Period 3 may have their dose escalated to ixekizumab 80 mg Q2W if the investigator determines that the patient may benefit from an increase in frequency of dosing to achieve adequate disease control. However, for patients in Group B, escalation to ixekizumab 80 mg Q2W may occur only after the patient has been retreated upon flare with the ixekizumab treatment regimen received during Period 1 (ixekizumab 80 mg Q4W) for at least 12 weeks.
- e For patients who were receiving ixekizumab in the originating study, the dose in the 24-week Lead-In Period (Period 1) will be based on the current dosing in the originating study. For patients in Study RHBX who were on placebo, patients will receive ixekizumab 80 mg Q4W.

## 5.2. Determination of Sample Size

It is estimated that approximately 750 patients will enter the long-term extension study (RHBY) after completion of Studies RHBV, RHBW, or RHBX. This sample size is estimated based on the 1-year retention rates from ixekizumab psoriasis studies and from 1 secukinumab radiographic (rad)-axSpA study (Baeten et al. 2015), which had a retention rate of approximately 85%. It is anticipated that approximately 30% of the 750 patients will meet the entry criteria for randomized-withdrawal (Sieper et al. 2015). Approximately 100 patients who achieved a state of sustained remission on IXE80Q4W will be randomized in a 2:1 ratio to IXE80Q4W or placebo, and approximately 100 patients who achieved a state of sustained remission on IXE80Q2W will be randomized in a 2:1 ratio to IXE80Q2W or placebo in the double-blind RWR period. This total sample size of 200 will provide over 99% power to detect a difference in the proportion of patients who do not experience a flare between the Combined Ixekizumab treatment group (including Q2W and Q4W) and placebo using a 2-sided Fisher's exact test at the 0.05 level, assuming the flare rates are 10% for ixekizumab and 70% for placebo. Sample size and power calculations are calculated using nQuery+nTerim 3.0.

## 5.3. Method of Assignment to Treatment

During the Lead-In Period (Period 1), patients who are previously receiving ixekizumab treatment during Studies RHBV and RHBW will, as of Week 0 in Study RHBY, continue to receive the same ixekizumab treatment regimen they are on at the end of the originating study, but now in open-label fashion.

For patients who are previously in Study RHBX, treatment during the Lead-In Period will be assigned as follows:

- patients who are rescued to open-label IXE80Q2W will remain on IXE80Q2W in open-label fashion.
- patients who are receiving blinded treatment with either IXE80Q2W or IXE80Q4W will continue on their ixekizumab dose regimen in blinded fashion.
- patients who are receiving blinded treatment with placebo will be assigned to receive blinded treatment with IXE80Q4W.

During the Extension Period, including RWR (Period 2), patients in Group A who do not meet entry criteria for RWR will continue to receive the same ixekizumab dose regimen that they are receiving during the Lead-In Period (IXE80Q2W or IXE80Q4W).

During the Extension Period, patients in Group B who have achieved a state of sustained remission, and meet the criteria for randomized withdrawal (RW) (see Section 5.1), will be assigned to treatment groups as follows by a computer-generated random sequence using an interactive web-response system (IWRS).

- Patients in the IXE80Q2W treatment group will be re-randomized to either IXE80Q2W or placebo at 2:1 ratio allocation and will be stratified by region and originating study.

- Patients in the IXE80Q4W treatment group will be re-randomized to either IXE80Q4W or placebo at 2:1 ratio allocation and will be stratified by region and originating study.

The IWRS will be used to assign double-blind investigational product to each patient. Site personnel will confirm that they have located the correct investigational product package by entering a confirmation number found on the package into the IWRS.

During the Long-Term Extension Period (Period 3), patients will continue the same treatment that they are receiving at the end of Period 2.

## 6. A Priori Statistical Methods

### 6.1. General Considerations

Statistical analysis of this study will be the responsibility of Eli Lilly and Company (hereafter, Lilly). The statistical analyses will be performed using SAS® Version 9.4 or higher.

Continuous data will be summarized in terms of the number of observations, mean, standard deviation (SD), minimum, median, and maximum. The minimum and maximum will be reported to the same number of decimal places as the raw data recorded in the database. The mean and median will be reported to 1 more decimal place than the raw data recorded in the database. The SD will be reported to 2 more decimal places than the raw data recorded in the database. In general, the maximum number of decimal places reported shall be 4 for any summary statistic.

Categorical data will be summarized in terms of number of patients in the analysis population, number of patients providing data at the relevant time point, frequency counts, and percentages corresponding to the appropriate method. Percentages will be presented to 1 decimal place. Percentages will not be presented for zero counts. For condition/event that is gender-specific (as defined by the Medical Dictionary for Regulatory Activities [MedDRA]), the denominator and computation of the percentage will include only patients from the given gender.

Change from baseline will be calculated as: observed postbaseline scores – baseline score.

For selective efficacy measures (including ASAS40 components, BASDAI score), percent improvement will be calculated as  $100 \times (\text{baseline score} - \text{observed scores})/\text{baseline score}$ , unless otherwise specified. If a patient has experienced an improvement, this measure will be positive. If a patient has experienced a worsening, this measure will be negative.

Unless otherwise specified, baseline for effect in efficacy and health outcomes analyses is defined as the last available value before the first dose of study treatment in Period 2 from the originating study and, in most cases, will be the value recorded at Week 0 from the originating study. For safety analysis, baseline is defined as the last available value before the first dose at the start of each analysis period of interest in RHBY. For safety analyses using a baseline period, the baseline period is defined as the entire period, that there is no drug dispensed in, prior to the first injection of the drug in the analysis period of interest.

All confidence intervals (CIs) and statistical tests will be 2-sided with an  $\alpha$  level of 0.05, unless otherwise specified. P-values which are  $\geq 0.001$ , and  $\leq 0.999$ , will be presented to 3 decimal places. All other p-values which are less than 0.001 will be presented as  $< 0.001$ , while p-values greater than 0.999 will be presented as  $> 0.999$ . Confidence intervals will be presented to 1 more decimal place than the raw data.

Age, sex, and race will be reported on all by-patient listings unless otherwise specified. Sex will be abbreviated as follows: female (F) and male (M). Race will be abbreviated as follows: American Indian or Alaska Native (AI), Asian (AS), Black or African American (BL), Native Hawaiian or other Pacific Islander (NH), White (WH), and Multiple (MU).

Section 6.1.1 describes the populations for analyses and [Table RHBY.6.1](#) displays analysis purpose, treatment groups, and group comparisons for each analysis period and analysis population.

### **6.1.1. Analysis Populations**

The following analysis populations will be used to address the study objectives.

**Lead-In Period Safety Population:** Unless otherwise specified, safety summaries for Combined Periods 1, 2, and 3 will be conducted on the Lead-In Period Safety Population, defined as all patients who receive at least 1 dose of ixekizumab in Period 1 in RHBY. Patients who do not meet entry criteria for participation in the randomized withdrawal-retreatment period (Group A) will continue to receive ixekizumab 80 mg Q2W or ixekizumab 80 mg Q4W. Patients who meet the entry criteria (Group B) may be randomized to ixekizumab or placebo at Week 24. Patients randomized to placebo may be retreated upon flare with the ixekizumab regimen that they received in Period 1. The data while on placebo is not included in the combined period analysis. For immunogenicity data analysis during the combined periods 1, 2, and 3, all data will be included regardless of being re-randomized to placebo or ixekizumab. Patients will be analyzed according to the treatment they were receiving at the start of Period 1.

**Long-Term Ixekizumab Treatment Efficacy Population:** Unless otherwise specified, efficacy and health outcome for Combined Periods 1, 2, and 3 will be summarized for the Long-Term Ixekizumab Treatment Efficacy Population, defined as patients who are randomized to ixekizumab 80 mg Q2W or ixekizumab 80 mg Q4W at Week 0 of the originating studies and consistently receive the same treatment regimen through Week 64 in RHBY. Patients who were randomized to placebo or adalimumab in any of the originating studies, patients who switched from IXEQ4W to open label to IXEQ2W during the originating study of RHBY, patients who were randomized to placebo during Period 2 of RHBY, and patients who were retreated during Period 2 of RHBY are not included in this population. Patients will be analyzed according to the ixekizumab regimen they were randomized to at Week 0 of the originating study.

**Ixekizumab Structure Population:** The analysis of 2-year radiographic progression in spine, measured by the change in mSASSS in patients with active rad-axSpA, will be conducted on Ixekizumab Structure Population, defined as all patients who i) are from either RHBV or RHBW study; and ii) have mSASSS data at both Week 0 in the originating study and Week 56 in RHBY.

**Randomized Withdrawal (RW) Intent-to-Treat (ITT) Population:** Efficacy and health outcome analyses for Period 2 will be conducted on RW ITT Population, defined as all patients who achieved a state of sustained remission and were randomized to 40-week double-blind placebo-controlled RWR period (Group B), even if the patient does not receive the correct treatment or otherwise does not follow the protocol. Patients will be analyzed according to the treatment to which they are assigned.

**RW Safety Population:** Safety analyses will be conducted on the RW Safety Population, defined as all randomized patients in Group B who have received at least 1 dose of study

treatment after randomization in the specified period. Patients will be analyzed according to the treatment to which they are assigned.

**Flare Population:** Defined as all randomized patients in Group B who experience a flare after randomization at Week 24. Efficacy summaries will be conducted for Period 2 and Combined Periods 2 and 3 on the Flare Population who receive at least one injection of ixekizumab retreatment after flare in the Combined Periods 2 and 3. Patients will be analyzed according to the treatment to which they are assigned at randomization and the retreatment.

**Dose Escalation Population:** Exploratory efficacy summaries will be conducted for Period 3 on Dose Escalation Population, defined as all patients (from Group A and Group B) who have been treated ixekizumab 80 mg Q4W for at least 12 weeks, and had their dose escalated to ixekizumab 80 mg Q2W (determined by investigator).

**Follow-Up Period Population:** Safety analysis for Period 4 will be conducted on the Follow-Up Period Population, defined as all patients who have completed an originating study (RHBV, RHBW, or RHBX) through Week 52 and have entered the Post-Treatment Follow-Up Period (Period 4) in RHBY. Patients will be analyzed according to the treatment they are taking before entering Period 4.

[Table RHBY.6.1](#) displays analyses purpose and treatment groups for each analysis population and study period.

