7.4. Dosage Modification

As described in Section 5.1, if a patient who has achieved a state of sustained remission (Group B) during the randomized withdrawal-retreatment period experiences a flare and meets the criteria for retreatment, the patient will be retreated with the ixekizumab treatment regimen that he or she was receiving prior to withdrawal (ixekizumab 80 mg Q2W or ixekizumab 80 mg Q4W). During Period 2, retreatment will begin at the next scheduled visit. During Period 3, given the longer interval between visits, retreatment may begin at the next scheduled visit or at an unscheduled visit prior to the next scheduled visit.

As of Week 64, patients in Group A receiving ixekizumab 80 mg Q4W may have their dose escalated to ixekizumab 80 mg Q2W in Period 3 if the investigator determines that the patient may benefit from an increase in frequency of dosing to achieve adequate disease control. Dose escalation may begin at the next scheduled visit or at an unscheduled visit prior to the next scheduled visit.

As of Week 64, patients in Group B ([Table RHBY.3](#)):

- who are receiving placebo will remain on placebo, and will be monitored per the Schedule of Activities (Section 2) for eligibility (i.e., flare) to be retreated with the ixekizumab treatment regimen they were receiving prior to withdrawal (ixekizumab 80 mg Q2W or ixekizumab 80 mg Q4W).
- who are receiving ixekizumab 80 mg Q4W may have their dose escalated to ixekizumab 80 mg Q2W in Period 3 if the investigator determines that the patient may benefit from an increase in dosing to achieve adequate disease control. Escalation to ixekizumab 80 mg Q2W may occur only after the patient has been retreated upon flare with the ixekizumab treatment regimen received during Period 1 (ixekizumab 80 mg Q4W) for at least 12 weeks.
- who are receiving ixekizumab 80 mg Q2W will remain on this dose until completion of the study or early discontinuation.

Table RHY.3. Dosage Modification for Group B during Period 2 and Period 3

Period 1 (Open-Label)	Period 2 (Blinded)	Period 3 (Blinded)	If Flare during Period 2 or 3, Retreat (Open-Label)	12 Weeks after Retreat, Escalate (Period 3) (Open-Label)
ixekizumab 80 mg Q2W	ixekizumab 80 mg Q2W	ixekizumab 80 mg Q2W	ixekizumab 80 mg Q2W	N/A
	placebo	placebo	ixekizumab 80 mg Q2W	N/A
ixekizumab 80 mg Q4W	ixekizumab 80 mg Q4W	ixekizumab 80 mg Q4W	ixekizumab 80 mg Q4W	ixekizumab 80 mg Q2W
	placebo	placebo	ixekizumab 80 mg Q4W	ixekizumab 80 mg Q2W

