### **6.1.2. General Considerations for Analyses during the Combined Periods 1, 2, and 3**

Combined Periods 1 and 2 starts at the first injection of IXE80Q2W or IXE80Q4W in RHYB, and ends on the injection date of Week 64 (Group A: Visit 10/Group B: Visit 515) or next injection date after Week 64 if injection date of Week 64 is missing which is the start date of Period 3, or at ETV prior to Week 64.

Combined Periods 1, 2, and 3 starts at the first injection of IXE80Q2W or IXE80Q4W in RHYB, and ends on the date of Week 104 visit (Group A: Visit 14/Group B: Visit 519) or at ETV prior to Week 104.

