#### **6.1.2.2. Long-Term Ixekizumab Treatment Efficacy Population**

Efficacy and health outcome data will be summarized for the Long-Term Ixekizumab Treatment Efficacy Population (see definition in Section 6.1.1) from Week 0 in the originating study to the visit at Week 64 and Week 104, respectively, in RHYB. For patients who were escalated from ixekizumab 80 mg Q4W to ixekizumab 80 mg Q2W after Week 64, only data while on ixekizumab 80 mg Q4W will be included. If the patient early terminates the originally assigned treatment (including retreatment and escalation) prior to Week 104, then the modified nonresponder imputation (mNRI) method will be applied for categorical endpoints, and modified baseline observation carried forward (mBOCF) will be applied for continuous endpoints from the early termination visit through Week 104.

The long-term treatment effect on a categorical variable is measured by the proportion of patients who have achieved or maintained a response (see algorithm in [Table RHY.6.4](#)) through Week 64 and Week 104, respectively, and the long-term treatment effect on a continuous variable is measured by change (or percent improvement) from baseline in the originating study.

The long-term treatment effect in categorical variables using observed cases, and continuous variables using observed cases and mBOCF will be summarized (as described in Section [6.1](#)) by treatment group (see [Table RHY.6.1](#)) at each scheduled visit from Week 0 in originating study. An alternative method to handle the missing data after Week 64 for the period of Week 0 in the originating study to Week 104 in RHY, mNRI method will be applied for categorical variables and mixed model for repeated measures (MMRM) will be applied for continuous variables. Data will also be summarized graphically using the response rate for categorical variables and mean for continuous variables by group at each scheduled visit. The time points during the Extension Period (Period 2) will follow the scheduled visits for group A patients with between-visits-interval of 8 weeks.

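### In the Combined Periods 1, 2 and 3 safety tables, exposure and events after escalation from Q4W to Q2W are reported in the Q4W column

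*SAP*

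**What the plan says.** SAP 6.1.1 sets the column for the Lead-In Period Safety Population: "Patients will be analyzed according to the treatment they were receiving at the start of Period 1". The one exclusion it makes is for placebo: "The data while on placebo is not included in the combined period analysis". Table RHBY.6.1 gives these tables three columns: IXE80Q2W, IXE80Q4W and Total IXE.

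SAP 6.1.2 says that the longest of these analyses starts at the first RHBY injection "and ends on the date of Week 104 visit" (or at early termination). The shorter one, Combined Periods 1 and 2, starts at the same point "and ends on the injection date of Week 64".

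Escalation is possible inside the longer window. Protocol 7.4 says: "As of Week 64, patients in Group A receiving ixekizumab 80 mg Q4W may have their dose escalated to ixekizumab 80 mg Q2W". Footnote d to the design figure in SAP 5.1 adds that Group B may escalate only after a flare and at least 12 weeks of Q4W retreatment.

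Two other SAP rules treat the same patients differently. For long-term efficacy, SAP 6.1.2.2 says that once a patient is escalated "only data while on ixekizumab 80 mg Q4W will be included". For Period 4 safety, SAP 6.1.1 and 6.1.6 group patients by the treatment taken just before entering follow-up.

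**The concern.** A patient who starts on Q4W and escalates at Week 64 stays in the Q4W column until Week 104. Adverse events, patient-years and abnormal laboratory values that arise on the more frequent regimen are then read as Q4W results.

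Escalated patients are also a selected group, because the investigator has judged that more frequent dosing might bring adequate disease control. Leaving their later events under Q4W could hide a real difference related to dosing frequency, or could raise Q4W rates through selection. A reader of the table could not tell which.

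The labelling is also uneven within the SAP. A patient who finishes on escalated Q2W counts as Q4W in the combined safety table, leaves the long-term efficacy data at escalation, and counts as Q2W in Period 4.

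**Working it through.** **1. Length of the window.** Escalation is allowed from Week 64 and the analysis ends at Week 104: 104 − 64 = 40 weeks. The visit days in the Schedule of Activities agree: 728 − 448 = 280 days = 40 weeks. This reproduces the Period 3 length in SAP 5.1.

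**2. Most Q2W time one patient can carry in the Q4W column.**
- Group A: 40 weeks, if escalated at Week 64.
- Group B: earliest escalation = the later of Week 64 and (start of Q4W retreatment + 12 weeks). Retreatment by Week 52 gives 52 + 12 = 64, so 40 weeks. Retreatment at Week 64 gives 76, so 104 − 76 = 28 weeks. Retreatment at Week 76 gives 88, so 104 − 88 = 16 weeks.

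**3. Share of that patient's record (escalation at Week 64).** Time: 40/104 = 38.5%. Scheduled injections: 16 on Q4W before Week 64 (Weeks 0 to 60) and 20 on Q2W after (Weeks 64 to 102), so 20/36 = 55.6%. Dose: 36 × 80 = 2880 mg, against (16 + 10) × 80 = 2080 mg on Q4W throughout.

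**4. Share of the Q4W column.** Let f be the fraction of Q4W patients who escalate. The documents do not give f, so it is assumed. With full follow-up and no placebo time, the share is f × (104 − escalation week)/104.

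| f (assumed) | Week 64: f × 40/104 | Week 76: f × 28/104 | Week 88: f × 16/104 |
|---|---|---|---|
| 10% | 3.8% | 2.7% | 1.5% |
| 30% | 11.5% | 8.1% | 4.6% |
| 50% | 19.2% | 13.5% | 7.7% |

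Week 64 is the earliest possible date, so under those assumptions its column is the upper bound for each f. Drop-out after escalation would lower the share. Early drop-out or removed placebo time among the other Q4W patients would shrink the denominator and raise it.

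**5. What this would do to a rate.** Suppose, for illustration, that the true event rate on Q2W were twice that on Q4W, constant over time and without selection. With share s from the Week 64 column, the Q4W column would show 1 + s times its true rate, and the apparent ratio would be 2/(1 + s). This gives 2/1.038 = 1.93, 2/1.115 = 1.79 and 2/1.192 = 1.68 for f = 10%, 30% and 50%.

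**6. Whether another rule corrects it.**
- SAP 6.13.1 has one exposure formula for an uninterrupted ixekizumab regimen and one for patients randomized to placebo. Neither stops at escalation.
- SAP 6.1.2.1 fixes the laboratory and vital-sign baseline before Period 1 despite later regimen changes. It resets the adverse-event baseline only for placebo patients who are retreated.
- The Dose Escalation Population (SAP 6.1.1, 6.1.5.1, Table RHBY.6.1) has efficacy summaries only, and SAP 6.14.2 plans no safety subgroups.
- The Period 3 adverse-event summary for randomized patients uses assigned treatment, so it does not isolate the escalated time either.

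**The case against.** Analysis by starting regimen is a recognised convention, the SAP states it openly, and it keeps complete follow-up of each starting group. The efficacy cut answers a different question, maintenance on a constant regimen, so it does not bind the safety tables. This stands as a reason to keep the column. It does not make that column sufficient alone, because the same tables already drop placebo time and so are partly on-treatment.

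A reader might infer that the only long-term safety comparison by dose is spoiled. The documents do not support that. Combined Periods 1 and 2 has the same columns and stops before escalated dosing can contribute. SAP 6.13.2 also plans an overall adverse-event summary by treatment group for the Long-Term Ixekizumab Treatment Efficacy Population, although it does not say whether that summary is cut at escalation.

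Nor is a clean dose comparison being lost. Patients rescued to Q2W in RHBX enter as Q2W, and RHBX placebo patients enter as Q4W, so the columns are not a randomized contrast.

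Replacing the column by truncated Q4W time would bring its own bias. Patients chosen for inadequate control would leave, and the remaining Q4W time would favour well-controlled patients. This also stands, and it shapes the remedy.

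Escalation is partly visible already: total dose counts actual active injections, and by-patient listings cover all adverse events. That shows extra drug in the Q4W column but does not tie events to it.

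**Conclusion.** The mislabelling is real and follows from an explicit rule, but it is confined to the IXE80Q4W and IXE80Q2W columns of one set of descriptive tables, those for Combined Periods 1, 2 and 3. At most 40 weeks per patient is affected, and less for late escalation or for Group B flares in Period 3. At column level the upper bounds are 3.8%, 11.5% and 19.2% for assumed escalation rates of 10%, 30% and 50%, given escalation at Week 64, full follow-up and no placebo time.

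Two stronger readings should be avoided. The first is that a safety conclusion or test is at risk. Protocol 10.3.4 bases the primary safety analyses on Period 2, before escalation is allowed. Total IXE is unchanged, and no primary or major secondary test uses these tables. The second is that no analysis anywhere separates post-escalation safety. The SAP contents list a table of planned exploratory analyses (Table RHBY.6.12) whose section is blacked out, so the statement holds only for the visible text.

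**What to change.** In SAP 6.1.1 and 6.13.1, keep the column by starting regimen and, for Combined Periods 1, 2 and 3, add a second display:

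- Present exposure-adjusted adverse-event summaries with Q4W time ended at the first Q2W injection, and a separate column for Q4W escalated to Q2W. Exposure adjustment is needed because the segments differ in length. A safety summary for the already defined Dose Escalation Population would serve the same purpose as the new column.
- Set the adverse-event baseline for the escalated segment just before the first escalated injection, following the rule that SAP 6.1.2.1 already uses for retreatment after placebo.
- Note under the table that the truncated Q4W time is selected for better-controlled patients and that the two displays should be read together.

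The cost is some programming and probably small numbers in the new column. The data are already collected, and trial conduct does not change.
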